UNIVERSITY OF SAO PAULO
SCHOOL OF MEDICINE OF RIBEIRAO PRETO

[name]

Randomized, placebo-controlled study of corticosteroid therapy for persistent interstitial disease post-COVID-19.

Ribeirao Preto

2021

Abstract

Introduction: The new coronavirus (SARS-CoV-2) is a virus with an intense capacity for dissemination and high mortality rate. The main cause of death is viral pneumonia, characterized as organizing pneumonia that responds to treatment with corticosteroids. After 1 month of the acute phase, 25% of patients have complete recovery from lung lesions. However, lung lesions can evolve as persistent interstitial lung disease; it is possible that this persistent disease is also responsive to corticosteroid therapy. There are no controlled and randomized studies on any treatment and its effect on the natural history of this subacute or late manifestation of COVID-19.

Objective: To understand the effect of oral corticosteroid therapy in the treatment of persistent pulmonary manifestations (clinical and radiological) in patients who had moderate, severe, and critical forms of COVID-19. To understand the role of some risk factors in the development of this form of lung disease. To add information on the natural history of interstitial lung disease secondary to SARS-CoV-2 pulmonary infection.

Methodology: Randomized, double-blind, placebo-controlled study of patients who had COVID-19 viral pneumonia. Patients included after 12 weeks of COVID-19 diagnosis with RT-PCR or imaging tests that confirm the infection for inclusion in the protocol 100 patients with changes in high-resolution chest tomography and diffusion spirometry, will be divided into two groups, placebo and treatment; the treatment group will receive prednisolone at a dose of 0.5 mg/kg/day for 1 month and weaning in 30 days. Clinical, laboratory, functional, and imaging evaluations will be performed at the beginning, after 3 and 6 months of treatment and monthly telephone calls.

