The identification of the bottles and the preparation of the placebo tablets will be carried out by a compounding pharmacy that will identify the labels by codes, and a researcher on the team will learn the content related to each code (placebo or prednisolone). This researcher will not have access to the study care or procedures.

Patients who received placebo took a similar number of tablets for similar time span.

Visits/Protocol: After 12 to 20 weeks of the diagnosis of pneumonia caused by the new coronavirus patients will be a standardized time. A medical evaluation, laboratory, imaging, and functional tests will be carried out with a view to immediate entry into the study. This will be considered the first visit. Patients will be randomized, and treatment will be given on the first visit. The evaluations will be carried out on this first visit (baseline) and will be repeated after 3 and 6 months from the first visit. The recruitment period will be 12 months, and the follow-up period for each patient will be 9 months. Depending on the study outcomes and the interest of the research team, this follow-up may be extended through a new research project.

In addition to quarterly assessments, these patients will be assisted with monthly telephone calls to check adherence and possible adverse effects.

If any patient is still using corticosteroid therapy, they will also be randomized and will be instructed to wean off the corticosteroid in use within 15 days and will receive the study treatment while reducing the dose of the previous corticosteroid until it is completely removed.

Randomization

Numbers 1 to 100 were randomly mixed up using a computer randomizer program. The first fifty were allocated as placebo and the last fifty as Treatment. Included patients received a number consecutively from 1 to 100. Only one researcher ([name]) knew to which group every number (patient) belonged, placebo or Treatment. This researcher labeled medicine vials accordingly.

Patients

One hundred patients will be included in the study, of which 50 will be in the control group and 50 in the treatment group.

Inclusion criteria:

- Over 18 years of age;
- Diagnosis of COVID-19 by RT-PCR (Reverse transcription polymerase chain reaction), a test that detects the presence of viral antigen in nasal and oropharyngeal secretions or chest tomography typical of COVID-19 according to radiological standardization for COVID-19 cases (Machnicki, 2021);

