- Pulmonary involvement with persistent disease identified on high-resolution computed tomography of the chest;
- Reduction in DLCO (percentage of predicted), with measurements less than or equal to 80%.

Exclusion criteria

- Previous diagnosis of pulmonary embolism;
- Previous and decompensated heart failure with electrocardiographic changes, chest X-ray with increased cardiac silhouette, and signs in the clinical examination suggestive of heart failure;
- History of acute myocardial infarction in the last month or angina pectoris; Absolute contraindications to the use of corticosteroids or other comorbidities that prevent the use of corticosteroids such as uncontrolled diabetes, untreated glaucoma, current infections such as pneumonia or tuberculosis, and untreated psychiatric disorders;
- Pregnancy and lactation;
- Inability to perform stress tests such as walking tests and spirometry due to critically ill neuropathy or sequelae of stroke, among other limiting pathologies.

The patient will be informed of the risks related to corticosteroid treatment, and this information will be included in the consent form.

Structured Clinical Assessment

The initial, 3-month and 6-month assessments will include the following tests:

1 - ASSESSMENT OF LUNG FUNCTION

- Spirometry with CO (carbon monoxide) diffusion and lung volumes

The spirometry test will be performed in the pulmonology department using a carbon monoxide diffusion device. To perform the test, the patient will be instructed to sit upright, and a nose clip will be used. The technique used must follow standards of reproducibility, acceptability, and predictive value parameters for age, sex, and height, which will follow the guidelines of the American Thoracic Society/European Respiratory Society Statement/ERS 2005 (MILLER et al., 2005). Simple spirometry with the use of bronchodilator (pharmacodynamic test)

The simple spirometry test will be performed simultaneously with the diffusion test in the pulmonology department. The technique performed must follow reproducibility and acceptability standards, and the predictive value parameters for age, sex, and height will be followed according to the American Thoracic Society/European Respiratory Society Statement 2005 (MILLER et al., 2005).

2 - FUNCTIONAL CAPACITY TEST

- 6-Minute Walk Test

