- level of urea, LDH, and D-dimers at hospital admission;
- History of smoking;
- History of alcoholism;
- Symptoms persisting after hospital discharge secondary to COVID-19 infection: chronic cough, dyspnea on exertion (dyspnea classification by MRC - appendix 2), chest pain, chronic fatigue, and joint pain.

Follow-up telephone calls will be made monthly to increase adherence and check for possible adverse effects of corticosteroid use.

Ethical aspects

The project will be submitted for review by the Research Ethics Committee of the Hospital das Clínicas de Ribeirão Preto through the Plataforma Brasil. Information about the objectives, procedures, risks, and benefits of the study will be passed on to patients, and upon their agreement to participate, they will be invited to sign an informed consent form (ICF).

Statistical analysis

ANOVA was used to assess continuous variables (FEV1 liter, FEV1%, FVC liter, FVC%, TLC liter, TLC%, DLCO, MIP, MEP, 6MWT distance, ESR, CRP, D-dimer).

SF-36 scores were analyzed using a negative binomial regression model with repeated measures and a logarithmic link function, given that we can consider these outcomes as discrete and non-continuous quantitative variables. This model was used because the assumptions of normality and homoscedasticity of residues for the ANOVA analysis were not valid. From the model estimates, the relative increase (or

reduction) in the mean was calculated based on the expression $AR(\beta) = [\exp(\beta) - 1]*100\%.$

MRC dyspnea score and PCFS scale are ordinal categorical variables; the analysis used an ordinal multinomial regression mode, which estimates the odds ratio of higher "scores", meaning worse.

The analysis of the dichotomized PCFS used a log-binomial regression model, which estimates the prevalence ratio of grade 3 or 4 occurring between groups and times.

Reference

BORG G. Psychophysical scaling with applications in physical work and the perception of exertion. **Scand J Work Environ Health**. 1990 16 Suppl 155-8. doi: 10.5271/sjweh.1815. PubMed ID: 2345867

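### The plan collects baseline values for 11 of its 13 continuous outcomes but names no baseline covariate, ANOVA type or treatment contrast; baseline-adjusted analysis would add precision at no cost in patients or visits

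*Combined protocol and SAP*

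**What the plan says.** The schedule is stated three times and consistently. Abstract, Methodology: "Clinical, laboratory, functional, and imaging evaluations will be performed at the beginning, after 3 and 6 months of treatment". Visits/Protocol: "The evaluations will be carried out on this first visit (baseline) and will be repeated after 3 and 6 months from the first visit". Structured Clinical Assessment: "The initial, 3-month and 6-month assessments will include the following tests". The tests named in the Abstract and under Structured Clinical Assessment cover FEV1, FVC, TLC, DLCO, 6-minute walk distance, ESR, CRP and D-dimer. MIP and MEP are not among them.

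The whole method for the continuous outcomes is one sentence in the Statistical analysis section, which reads: "ANOVA was used to assess continuous variables (FEV1 liter, FEV1%, FVC liter, FVC%, TLC liter, TLC%, DLCO, MIP, MEP, 6MWT distance, ESR, CRP, D-dimer". It gives no factors, time structure, contrast or covariate.

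Two other sentences in that section bear on how the ANOVA might be read. For SF-36: "SF-36 scores were analyzed using a negative binomial regression model with repeated measures and a logarithmic link function", with the reason "This model was used because the assumptions of normality and homoscedasticity of residues for the ANOVA analysis were not valid". For the dichotomised PCFS, the model is one "which estimates the prevalence ratio of grade 3 or 4 occurring between groups and times".

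Under Patients, the sample is 100, 50 per arm. The inclusion criteria require DLCO at or below 80% of predicted.

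**The concern.** With 50 patients per arm, precision is limited. The Methodology admits patients ranging from those treated as outpatients to those who were intubated, so differences between patients are likely to be wide. A baseline measurement of the same quantity removes part of that spread from the treatment comparison, and this trial already collects one for most of its continuous outcomes. The plan does not say that it will use it.

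The bare word ANOVA also leaves open which number is the treatment effect. The candidates (difference at a visit, change from baseline, group-by-time interaction, group main effect) have very different power under the same true effect. The interaction test also has a condition for its error rate that the plan does not mention.

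**Working it through.** **Inputs from the documents.** 50 per arm; visits at baseline, 3 and 6 months; 13 ANOVA variables. Removing MIP and MEP leaves 13 − 2 = 11 with a documented baseline.

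**Inputs assumed, because the documents give none.** Effect 0.5 SD, present at both follow-up visits; two-sided 5%; no dropout; equal SD at each visit; correlation ρ between any two visits of 0.3 / 0.6 / 0.8. The plan has no power calculation to reproduce.

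**Step 1: variance at one follow-up visit.** The variance of the estimated difference is (2/50) × factor, in SD² units.
- Follow-up only: factor 1.
- Change score: 2(1−ρ) = 1.40 / 0.80 / 0.40.
- ANCOVA: 1−ρ² = 0.91 / 0.64 / 0.36.

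The ANCOVA saving is ρ² = 9 / 36 / 64% against follow-up only. Against a change score it is 1 − (1+ρ)/2 = (1−ρ)/2 = 35 / 20 / 10%.

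**Step 2: group main effect of a repeated-measures ANOVA over all three visits.** The true differences are 0, 0.5 and 0.5, so their average is 1/3 SD. The variance factor of a patient's three-visit mean is (1+2ρ)/3 = 0.533 / 0.733 / 0.867.

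**Step 3: power and precision.** Noncentral t, with noncentrality effect / √(2 × factor/50), on 98 df (97 for ANCOVA). The half-width is t × √(2 × factor/50).

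| Analysis | Power, ρ = 0.3 / 0.6 / 0.8 | 95% CI half-width (SD) |
|---|---|---|
| Follow-up only | 70% at every ρ | 0.40 |
| Change score | 55 / 79 / 97% | 0.47 / 0.36 / 0.25 |
| ANCOVA | 74 / 87 / 98% | 0.38 / 0.32 / 0.24 |
| Group main effect, three visits | 62 / 49 / 43% | not comparable (different estimand) |

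A simulation of 8,000 trials per setting gave ANCOVA power of 72.1 / 87.0 / 98.6%, with type I error 5.1 to 5.2%.

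**Step 4: both follow-up visits, like with like.**
- Group-by-time F(2,196): the squared deviations of 0, 0.5, 0.5 from their mean sum to 1/6, so the noncentrality is 25 × (1/6)/(1−ρ) = 5.95 / 10.42 / 20.83. Power is 57 / 83 / 99%.
- Joint 2-df test of the two baseline-adjusted differences, F(2,96): the noncentrality is 25 × 0.5/[(1−ρ)(1+2ρ)] = 11.16 / 14.20 / 24.04. Power is 85 / 92 / 99%.

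**Step 5: error rate of the uncorrected group-by-time F.** Step 4 assumes equal correlations, which satisfies sphericity. If instead the two follow-up visits correlate 0.9 with each other and the baseline correlates 0.6 or 0.4 with them (assumed values), 20,000 simulated null trials give type I error of about 6.7% and 7.3%. The Monte Carlo error is √(0.07 × 0.93/20,000), about 0.2 points.

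**The case against.** The strongest reply is that the ANOVA was probably repeated-measures, so the baseline is already used. The SF-36 model has repeated measures and replaced an ANOVA whose assumptions failed, and the PCFS model refers to times. This makes the repeated-measures reading plausible but does not prove it. If it is right, the gain is the smaller one: at ρ = 0.8 the half-width goes from 0.25 to 0.24 SD. That part of the objection stands, and the comparison with follow-up only should not be taken as the expected benefit. It does not remove the point, because a repeated-measures ANOVA still leaves the contrast unstated.

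It also stands that no correlation, SD, effect, alpha or dropout is given, so the gain cannot be derived from the documents. The 80% entry limit may lower the correlation for DLCO and shrink its gain.

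A reader might infer three stronger things. The first is that the ANOVA is wrong or treats visits as independent; the text does not show this, and a per-visit ANOVA or a properly specified repeated-measures ANOVA is valid. The second is that the false-positive rate is inflated. That requires an uncorrected interaction test and unequal correlations between visits, and the plan reports neither. The third is that the ordinal, log-binomial and SF-36 models share the fault; no claim is made about them here.

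**Conclusion.** The point holds as a free improvement and a specification gap, not as an error in the plan. ANCOVA is at least as precise as either a follow-up-only or a change-score analysis, apart from the negligible cost of one parameter, so the recommendation does not depend on which ANOVA was meant. Only the size of the gain does: under the assumptions above, 4 to 29 power points over follow-up only (74 − 70 to 98 − 69.7 before rounding) and 19 down to 1 over a change score as ρ rises from 0.3 to 0.8. The largest loss would come from reading the treatment effect off a group main effect that includes baseline, which the documents neither state nor exclude. Confidence is medium, because every quantitative input except 50 per arm is assumed.

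**What to change.** State which ANOVA is meant and which contrast is the treatment effect. For each continuous outcome with a baseline value, use one of two models:
- ANCOVA at each follow-up visit, with the baseline value as covariate; or
- a mixed model on the 3- and 6-month values with baseline, group, visit and group-by-visit, patient as the repeated unit and an unstructured covariance. This removes the reliance on sphericity.

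Take the between-arm differences at 3 and 6 months as the treatment effect. For ESR, CRP and D-dimer, use a log scale for both outcome and baseline if they are skewed. Say whether MIP and MEP have a baseline value.

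The cost is a few sentences of analysis plan and a few lines of code, with no new data, patients or visits. The Statistical analysis section is in the past tense and reports failed assumptions, so the analysis may already have been run. In that case, report the adjusted analysis beside the existing one and label it as added later.

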All questionnaires will be applied by the doctor responsible for the project, will be applied during the clinical evaluation, and will be part of the patient's anamnesis; the data obtained will be included in the medical record.

4 - MEDICAL EVALUATION AND LABORATORY TESTS

The medical evaluation includes anamnesis, clinical examination (clinical pulmonary and cardiac examination and general clinical examination, including weight and height measurements), and measurement of vital signs (heart rate, respiratory rate, oxygen saturation by pulse oximetry, blood pressure). The medical evaluation aims to identify changes in pulmonary auscultation and signs of chronic respiratory disease, in addition to evaluating other pathologies that may be grounds for exclusion from the research project, such as heart failure, pulmonary embolism, recent heart attack, inability to perform the proposed tests, such as neuropathy in critically ill patients.

Laboratory tests will be included to check for possible persistent inflammatory activity of the coronavirus in the body since there is still inflammatory lung disease. These tests include inflammatory markers, which are measurements of D-dimers, blood count, C-reactive protein, LDH, and erythrocyte sedimentation rate (ESR).

Some lung alterations may be pre-existing and secondary to pre-existing autoimmune diseases. Autoimmunity markers will be performed for differential diagnosis of autoimmune lung diseases: antinuclear factor (ANA) and rheumatoid factor (RF). If it is confirmed that these patients have interstitial lung disease associated with autoimmunity and overlapping with a disease secondary to SARS-CoV-2, these patients will be analyzed separately at the end of data collection.

The requested tests are part of the evaluation of patients who were hospitalized with a diagnosis of COVID-19 pneumonia and are included in the post-discharge reassessment routine.

A review of medical records to collect medical history and data on severity characteristics during hospitalization is necessary to obtain correlation data between this information and interstitial lung disease. The following variables will be evaluated to verify this correlation:

- sex, age, body mass index, previous diagnosis or during hospitalization of diabetes, systemic arterial hypertension;
- survey of intubation time and length of stay in the ICU bed;

- The extent of pulmonary involvement seen on tomography or chest X-ray at admission;

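### ESR, CRP and D-dimer are listed under ANOVA with no scale, transformation or baseline adjustment stated; a log-scale ANCOVA would be a cheap gain if they are right-skewed

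*Combined protocol and SAP*

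**What the plan says.** The protocol and SAP are one document. Under Statistical analysis, "ANOVA was used to assess continuous variables", and the variables listed run from FEV1, FVC, TLC and DLCO to "6MWT distance, ESR, CRP, D-dimer". The factors in the ANOVA, the contrast of interest, any covariate and the scale of analysis are not given.

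The next paragraph moves the SF-36 to a negative binomial model with a log link, on the ground that "the assumptions of normality and homoscedasticity of residues for the ANOVA analysis were not valid", and reports its effects as percentage changes in the mean. No residual check, passed or failed, is reported for the markers.

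On design, "One hundred patients will be included in the study, of which 50 will be in the control group and 50 in the treatment group" (Patients), and the baseline evaluations "will be repeated after 3 and 6 months from the first visit" (Visits/Protocol). The purpose of the markers is given under Medical evaluation and laboratory tests: "Laboratory tests will be included to check for possible persistent inflammatory activity of the coronavirus in the body". No primary outcome, alpha, power, effect size or SD is stated for any variable.

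**The concern.** ESR, CRP and D-dimer cannot be negative. If their values have a long right tail and a spread that grows with the mean, a few high results dominate the arm means and widen the interval for the difference. A real proportional reduction can then be missed. The plan treats failed normality and unequal variance as decisive for the SF-36, but says nothing on the same question for the markers.

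At stake is the precision of the blood evidence on persistent inflammation, which is part of the reasoning for giving a corticosteroid. The sample size is fixed without a stated derivation, so the choice of analysis is one of the few places where precision can still be gained. The baseline value is already collected, yet the plan does not say that it is used.

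**Working it through.** **Nothing to reproduce.** The total of 100 has no stated derivation, and no power is given for a marker.

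**Inputs from the document.** n = 50 per arm; measurements at baseline, 3 and 6 months; ANOVA.

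**Assumed, because the document is silent.** Two-sided alpha 0.05; log-normal values with log-SD σ from 0.5 to 1.25; the same proportional effect in every patient, θ = 2/3; no dropout; correlation 0.5 between log baseline and log follow-up.

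**Log scale, follow-up values only.** Power ≈ Φ(|ln θ| / (σ√(2/n)) − 1.96), with |ln(2/3)| = 0.4055 and √(2/50) = 0.2.
- σ = 0.5: 0.4055/0.10 = 4.055; Φ(2.095) = 98%
- σ = 0.75: 0.4055/0.15 = 2.703; Φ(0.743) = 77%
- σ = 1.0: 0.4055/0.20 = 2.027; Φ(0.067) = 53%
- σ = 1.25: 0.4055/0.25 = 1.622; Φ(−0.338) = 37%

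**Measured scale, follow-up values only.** The squared coefficient of variation is exp(σ²) − 1, so roughly z = (1 − θ) / √[(exp(σ²) − 1)(1 + θ²)/n]. At σ = 1.0 this is 0.3333/√(1.718 × 1.444/50) = 0.3333/0.2228 = 1.50, and Φ(1.50 − 1.96) = 32%. This normal approximation is crude for skewed data, so the table uses simulated two-group tests.

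**With the log baseline as covariate.** Replace σ by σ√(1 − 0.5²) = 0.866σ. At σ = 1.0: 2.027/0.866 = 2.341; Φ(0.381) = 65%.

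Simulated power (a repeat with 40,000 trials per setting agrees to within about one point):

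| log-SD | Measured scale | Log scale | Gap | Measured-scale ANCOVA | Log ANCOVA | Gap |
|---|---|---|---|---|---|---|
| 0.5 | 96–97% | 98% | 1–2 | – | – | – |
| 0.75 | 66% | 76% | 10 | 75% | 87% | 12 |
| 1.0 | 37% | 52% | 15 | 42% | 63% | 21 |
| 1.25 | 21% | 37% | 16 | 24% | 46% | 22 |

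Baseline adjustment helps on either scale, so part of the step from 37% to 63% at log-SD 1.0 has nothing to do with logs. On the measured scale it does not close the gap.

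**If the contrast is change from baseline**, which the plan leaves open, the measured scale does worse: 90% against 98%, 50% against 76%, 26% against 53% and 15% against 36% at log-SD 0.5, 0.75, 1.0 and 1.25.

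**Type I error.** Under no effect, measured-scale ANOVA rejects in 5.4% of trials at log-SD 0.3, 4.9% at 0.5, 4.1% at 1.0 and 3.1% at 1.5. It becomes conservative rather than anti-conservative.

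**Where the ranking reverses.** Take log-SD 0.5, with 20% of control patients elevated four-fold and treatment normalising the corresponding patients. Power is then 78% on the measured scale and 58% on the log scale; with 30% elevated it is 97% against 87%. If treatment only narrows the distribution (log-SD 1.0 to 0.6, equal medians), it is 24% against 5%.

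**Assay limit.** With half of the control values below the limit and set to half of it (log-SD 1.0, same effect), the log-scale advantage shrinks from 15 to 9 points (41% against 32%).

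**The case against.** The strongest reply is that the measured scale is inferred from silence. ANOVA can be run on log values, and the SF-36 paragraph shows that residuals were examined for at least one outcome and the model changed when they failed. A reader might infer that the markers were analysed untransformed with their assumptions ignored; the document does not show that. What stands is that neither the scale nor a check is stated for them.

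Second, the skew is an outside assumption, and three different markers need not share one distribution. This stands too, and is why the cost is given as a range that includes almost nothing at log-SD 0.5.

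Third, log-normal data with a uniform proportional effect is the case the log-scale test suits best. The tests are there to look for persistent inflammation, so an effect confined to a minority with raised values is plausible, and there the log scale loses. It also changes the estimand from a difference in arithmetic means to a ratio of geometric means. This does not defeat the recommendation, but the measured-scale result should be kept beside it.

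Fourth, the objectives concern pulmonary manifestations, risk factors and natural history; the tests are described as part of the routine post-discharge reassessment, and no marker is named as primary. That limits the importance of the point.

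**Conclusion.** The point holds as a modest, conditional one. The plan lists ESR, CRP and D-dimer under ANOVA without a scale, transformation or baseline covariate, and does not apply to them the reasoning it uses for the SF-36. If the markers are right-skewed, the effect is proportional and the analysis is on the measured scale, 50 per arm gives up 1 to 2 points of power at log-SD 0.5 and about 10 to 16 points at log-SD 0.75 to 1.25 for a one-third reduction. With baseline adjustment on both scales (correlation 0.5), the gap is about 12 to 22 points at log-SD 0.75 to 1.25.

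Three stronger readings are not supported. The documents do not establish a substantial loss of power, because they give no marker distribution. False-positive findings are not a consequence, because type I error is not inflated. The log scale is not better under every effect pattern. This is an inexpensive improvement to supporting outcomes and does not threaten the trial's main conclusions.

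**What to change.** In the Statistical analysis section, take ESR, CRP and D-dimer out of the general ANOVA list and state that:

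- log-transformed values at months 3 and 6 are compared between arms with the log baseline value as covariate;
- results are reported as between-arm geometric mean ratios with 95% CIs;
- values below the assay limit follow a named rule (half the limit is one option), with the number affected given by arm and visit;
- residuals are checked for the markers as for the SF-36;
- the measured-scale difference, also baseline-adjusted, is a sensitivity analysis.

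If logs were already used, saying so and adding the baseline covariate is enough. The section is written in the past tense, so if marker results had been seen before the change, it should be dated and labelled as such.

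The cost is wording only: no new patients, visits or samples. Readers get a ratio instead of an absolute difference as the main result, in line with the relative effects the plan already reports for the SF-36. Power may be lower if the effect sits in a minority with high values, which the sensitivity analysis is there to show.

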To assess functional capacity and check whether desaturation will occur during exertion, will be performed the 6-minute walk test at the Rehabilitation Center of the Hospital das Clínicas in a flat corridor measuring 30 meters in length. Patients will be instructed and encouraged to walk as fast as possible for 6 minutes, using standardized phrases every minute. Initially, they will be kept at rest to observe oxygen saturation values through pulse oximetry (SpO2), respiratory rate (RR), blood pressure (BP), heart rate (HR), and sensations of dyspnea (DS), and lower limb fatigue (LLF) using the Borg CR10 scale (BORG, 1990). BP measurements will

be taken with the individual in a sitting position and verified at rest immediately after the test and in the first, third, and sixth minutes of recovery. The 6MWT will be applied according to the guidelines of the American Thoracic Society (CRAPO et al., 2002). The expected distance traveled will be calculated using the equation developed for the Brazilian population (BRITTO et al., 2013).

3 - EVALUATION OF SUBJECTIVE FUNCTIONALITY

- SF-36 Quality of life questionnaire related to respiratory diseases:

This questionnaire assesses the quality of life in the last 4 weeks and includes the following assessment items: functional capacity, limitation due to physical aspects, pain, general health status, vitality, social aspects, limitations due to emotional aspects and mental health (CICONELLI et al., 1999) (appendix 1).

- Medical Research Council (MRC) dyspnea severity classification (KOVELIS et al., 2008), classification indicated to verify dyspnea related to physical efforts performed by the patient, classification related to symptoms of the last two weeks (appendix 2). Its score ranges from zero to four depending on the presence of dyspnea related to the intensity of physical effort. The Post-COVID-19 Functional Status Scale (PCFS) will be applied to assess patients' functionality at all hospital visits (KLOK et al., 2020) (appendix 3). This is a scale for assessing functional status based on the patient's self-report. It is a scale with classifications regarding muscle weakness, fatigue, depression, anxiety, shortness of breath, and memory loss. Its score ranges from zero to four, with a score of zero indicating no functional limitation and a score of four characterizing patients with severe functional limitations that require assistance for self-care.

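### Dichotomised PCFS: name the between-arm ratio at each follow-up visit as the treatment effect and adjust it for baseline PCFS, with patient-clustered errors

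*Combined protocol and SAP*

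**What the plan says.** The Statistical analysis section gives one sentence to the dichotomised PCFS: a log-binomial model "which estimates the prevalence ratio of grade 3 or 4 occurring between groups and times". The sentence before it covers the MRC and PCFS scales in ordinal form: "the analysis used an ordinal multinomial regression mode, which estimates the odds ratio of higher" scores. It mentions neither groups nor times. The same section states a within-patient structure for one outcome only: "SF-36 scores were analyzed using a negative binomial regression model with repeated measures and a logarithmic link function".

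On data collection, Visits/Protocol says that the evaluations "will be repeated after 3 and 6 months from the first visit", and the section on subjective functionality says that PCFS "will be applied to assess patients' functionality at all hospital visits". That gives up to three PCFS records per patient. Treatment is handed out at the first visit, so the baseline record precedes any treatment effect. The Patients section sets the size at 100, "of which 50 will be in the control group and 50 in the treatment group".

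No section says which visit or contrast is the treatment effect on PCFS, whether baseline PCFS is an outcome record or a covariate, or how records from one patient are linked in this model.

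**The concern.** A ratio between times uses more than one record from the same patient, so the model has to do something about within-patient correlation. A ratio between groups can mean the arms at 3 months, the arms at 6 months, an average over visits, or a group-by-time ratio. These are different quantities, and the sentence does not choose between them. The baseline score is collected in everyone before treatment acts, and it is the obvious covariate for a randomised comparison with 50 patients per arm, but the plan gives it no such role.

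Two things are at stake. The first is which number will be read as the treatment effect, a choice that should not be left until the data are seen. The second is precision: where PCFS is at least moderately stable within patients, an arm ratio that ignores baseline gives up power that costs almost nothing to recover.

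**Working it through.** **Inputs from the documents:** 50 patients per arm; visits at 0, 3 and 6 months; log link. They give no PCFS prevalence, within-patient correlation, effect size or significance level, so there is no figure of the plan's own to reproduce.

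**Assumed:** two-sided 5%; grade 3-4 prevalence 15%, 30% or 45%; true ratio 0.5 at both follow-up visits; correlation 0.3, 0.5 or 0.7 between two of a patient's records when prevalence is equal at both; no missing visits.

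**1. Different readings give different answers.** Suppose 30% at baseline in both arms, then 25% and 20% in control and 15% and 10% in treated at 3 and 6 months.
- 3 months: 0.15/0.25 = 0.60
- 6 months: 0.10/0.20 = 0.50
- Both follow-up visits pooled: (0.15 + 0.10)/(0.25 + 0.20) = 0.56
- All three visits pooled: (0.30 + 0.25)/(0.30 + 0.45) = 0.73

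A chance imbalance at baseline also matters. With 24% treated v 36% control at baseline and 13.3% v 20% at 6 months, the 6-month ratio is 0.67. The group-by-time ratio is (0.133/0.20)/(0.24/0.36) = 1.00.

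**2. Arm ratio at one visit, unadjusted.** Each patient contributes one record, so within-patient correlation plays no part. Variance of the log ratio = (1-p1)/(50 p1) + (1-p2)/(50 p2). At 45% v 22.5%: 0.55/22.5 + 0.775/11.25 = 0.0244 + 0.0689 = 0.0933, so the standard error is 0.306. Power = Phi(0.693/0.306 - 1.96) = Phi(0.31), about 62%. Simulation gives 64-65%. Simulated type I error is 3.3-4.4%, so there is no distortion.

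**3. The same ratio adjusted for baseline.** Correlated binary data were generated from a latent normal model. A log-link Poisson GEE was fitted to the 3- and 6-month records with arm, visit, arm-by-visit and baseline PCFS 3-4, with patient-clustered errors.

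| 45% prevalence, ratio 0.5 | corr. 0.3 | 0.5 | 0.7 |
|---|---|---|---|
| 6-month power, unadjusted | 64-65% | 64-65% | 64-65% |
| 6-month power, adjusted | 67% | 77% | 86% |

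A separate run gave 70/76/87% adjusted v 64-67% unadjusted. In that run the paired gains on the same data sets were 3.1, 10.7 and 22.9 points at 45% prevalence; 2.7, 8.9 and 21.2 at 30%; and 0.1, 4.1 and 10.1 at 15%. Type I error with adjustment was 3.6-5.8% over both runs. Adjusted fits that could not be estimated (0-0.4% at 30-45% prevalence, 4-6% at 15% with ratio 0.5) count as non-rejections.

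**4. Time contrasts, if records were treated as independent.** For 6 months v baseline, or its difference between arms, the independence variance is too large by about 1/(1-rho). The true error of a nominal 5% test is then 2 x (1 - Phi(1.96/sqrt(1-rho))): 1.9%, 0.6% and 0.04% at correlation 0.3, 0.5 and 0.7. Simulated group-by-time error was 1.6-1.9%, 0.5% and under 0.1%, against 4.3-5.3% with clustered errors. Power at 45% prevalence was 44/44/41% under independence and 58/71/85% clustered.

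**5. What the correlation labels mean.** They hold where prevalence is equal at the two visits, as in the control arm. In the treated arm at ratio 0.5, the largest possible correlation between baseline (p) and follow-up (q = p/2) is sqrt[q(1-p)/(p(1-q))]. At 45% this is sqrt(0.225 x 0.55/(0.45 x 0.775)) = 0.60; at 30% it is 0.64 and at 15% it is 0.68. So 0.7 cannot occur there, and the actual treated-arm values are about 0.27, 0.44-0.45 and 0.56-0.61.

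**6. What the model in step 3 does not estimate.** It holds no baseline outcome record, so it yields no 6-month-v-baseline ratio. Its arm-by-visit term compares 6 with 3 months. With ratio 0.5 at both visits that term is ln(0.5/0.5) = 0. The losses in step 4 therefore belong to a different contrast, which needs its own fit.

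**The case against.** The case for leaving the plan alone is substantial. The section gives each outcome one to three sentences, and the ANOVA sentence is equally silent on repeated measures, so the omission may be brevity. Log-binomial names a distribution and a link; it does not assert independence. The randomised comparison at a single visit can be read from the model as worded and is not distorted. All of this stands.

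A reader might infer that, because repeated measures are stated for SF-36 and not for PCFS, the PCFS records were analysed as independent. The documents do not show that. A reader might also infer an inflated false-positive rate. Pooling an arm effect over three records with independence errors would indeed give a type I error of about 11-20% at correlation 0.3-0.7, but no section plans that contrast. Nor does the ordinal sentence support the same charge, since it names neither groups nor times.

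Against the remedy, it can be said that baseline adjustment is a choice rather than a correction, that it gains little at correlation 0.3, and that the section is in the past tense, so a covariate added now could be post hoc. The first two points limit the claim but do not remove it: the covariate is already collected and simulated error stays near nominal. The third is met by labelling the change and showing the unadjusted ratio beside it.

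**Conclusion.** The point holds as a worthwhile improvement, with medium confidence. It is not a demonstrated error. The plan leaves open which PCFS ratio is the treatment effect and makes no use of baseline as a covariate. Under the assumptions above, baseline adjustment adds about 3 to 23 points of 6-month power at 45% prevalence, depending on correlation, and about 0 to 10 points at 15%, where power is poor either way. The claim that intervals for change from baseline and group-by-time are too wide is conditional on records having been treated as independent, which the text does not establish. Prevalence, correlation and effect size are all assumed, and missing visits were not modelled. PCFS is not named primary anywhere, so the priority is modest.

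**What to change.** In the Statistical analysis section, define the treatment effect on dichotomised PCFS as the between-arm prevalence ratio of grade 3-4 at each follow-up visit. Estimate it from a log-link model of the 3- and 6-month records with arm, visit, arm-by-visit and baseline PCFS, with patient-clustered (robust) errors.

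If a change-from-baseline or group-by-time ratio is also reported, fit it separately on all three visits with patient-clustered errors, because the follow-up-only model does not estimate it. State in one sentence how within-patient correlation was handled; if it already was, that sentence closes that part of the point. If results are already known, label the baseline adjustment as post hoc and give the unadjusted ratio too.

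The cost is SAP wording and a re-run on data already collected. Some fits may not be estimable when grade 3-4 is rare, so name a fallback, such as the unadjusted ratio at each visit. Extending the approach to the ordinal MRC and PCFS scores is optional and was not simulated.
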